5.5 STRATEGIES FOR RECRUITMENT AND RETENTION

Potential volunteers for this study will be recruited from the greater Winston-Salem, NC metro area. This is a primary catchment area for Wake Forest Baptist Health, and remains a reliable source of participants for clinical trials conducted by members of this research team. Both Drs. [name] (obesity medicine) and [name] (endocrinology) have clinical programs in the WFBH system that can serve as a source of patients. Patients in these clinics who meet potential eligibility criteria to enroll will be invited to screen for the study. We will also screen medical records using i2b2 and the CTSI to identify potential participants who meet eligibility criteria. Individuals who are identified in the medical record screen will be invited to screen for the study via direct mail. In the direct mail invitation, participants will be able to complete a brief survey to indicate interest in screening for the study. One of the study team members will follow up with the potential volunteer by phone to complete a phone screen. If the potential participant passes the phone screen and is interested in proceeding, he/she will be invited to an in-person screening.

6 STUDY INTERVENTION(S) OR EXPERIMENTAL MANIPULATION(S)

6.1 STUDY INTERVENTION(S) OR EXPERIMENTAL MANIPULATION(S) ADMINISTRATION

6.1.1 STUDY INTERVENTION OR EXPERIMENTAL MANIPULATION DESCRIPTION

ACTIVE INTERVENTION

High intensity medical weight loss: Participants randomized to the HIWL treatment group will be placed on a meal replacement-based weight loss protocol. [name] will oversee the medical management team and implementation of this protocol at the Weight Management Center. He serves as the medical director for medical weight management and has over 13 years of experience treating a wide range of patients with a low calorie meal replacement protocol. Participants will consume a minimum of 80 grams of protein daily in 4-5 servings of meal replacement. Minimum caloric intake will be 960 kcal/day with adjustments to intake made based on BMI and activity levels, holding the percent of calories from protein constant at 35%. The meal plan provides 100% of daily recommended needs for micronutrients. Meal replacements will be supplied at no cost to the participant at weekly clinic visits. Meal replacements are in the form of shakes, soups, and meal bars. Participants will begin to incorporate food into their routine beginning at week 13 with guidance from a dietitian. From weeks 13-24, caloric prescriptions will be between 1100 to 1600 kcal/day, using a combination of meal replacements and food, for continued weight loss. Beyond week 25, caloric intake will be individually tailored to achieve continued gradual weight loss or maintenance of body weight based on individual weight loss goals. Minimum caloric intake during this third treatment segment will be 1200 kcal/day. Participants will be seen by a study team clinician weekly for the first 4 weeks of the treatment plan. This weekly follow up will allow the medical weight loss team the opportunity to assess early treatment response, assess for side effects, and adjust medications to avoid hypoglycemia, hypotension, and/or dehydration. The first month of treatment is also critical to identify potential non-responders and alter their treatment plan early on. Research suggests that treatment non-response in the first 4-12 weeks is associated with poor weight loss outcomes.^{20,21} Beyond this first month of scripted intervention, the team will use information from the digital platform (described below) to dictate the type and intensity of follow up. Key factors that will influence the treatment plan are treatment response including pace of weight loss and changes in glycemic control; engagement in key behaviors including self-monitoring and physical activity; and complexity of the participant's medical regimen including use of insulin, anti-hypertensives, or other medications that we adjust during weight loss.

Digital platform: Our active intervention will be delivered with the aid of a technology platform that will automate portions of the intervention and assist clinicians in tailoring treatment and responding to participant needs in a "just-in-time" manner that we frame as a "data-assisted approach." Consumer-centric healthcare models enabled by technology are a new frontier in healthcare. Rising healthcare costs, consumer adoption of smart-phones, and a shift toward value-based payment models designed to produce better health outcomes all contribute to this trend. Our partner technology provider is Carium. Carium's software product is a HIPAA compliant, cloud-based, flexible platform, accessible via mobile and web applications, that allows patients and providers to co-create personalized care plans that are

informed by data and enable continuous collaboration during the course of everyday life. Through just-in-time encouragement and information, automatic medication reminders, and secure communication with care providers, the application supports patients in achieving their health goals, maximizing medication adherence, and achieving optimal health outcomes. This approach moves our current treatment pathways from generalized protocols that try to anticipate patient needs based on average responses to customized treatment plans that amplify the reach and impact of the current provider team. This makes the proposed intervention highly scalable and sustainable in a value-based care world. The platform has been deployed in a variety of healthcare settings, including primary care practices, care management programs, and community centers. In addition to the software component, the Carium team provides expertise in clinical practice transformation, patient engagement, behavior change science, and the latest technology. Core capabilities of Carium's offer include integration with remote monitoring devices such as activity trackers (Apple HealthKit, FitBit, Google Fit, etc.), glucometers (Omron, Dexcomm, Contour, etc.), blood pressure cuffs (Omron, etc.), scales (FitBit, Omron, BodyTrace, etc.); surveys, interviews, and self-assessments; secure messaging (one-to-one and groups) (Figure 2); photo and text journaling; content management and sharing; data-driven reminders, rules, and alerts to enable habit-engineering and behavior change; automation for patient experience and care team efficiency; dashboards and reports on engagement, patient progress, outcomes, population health; and seamless integration into clinical EMR workflows.

Body weight: To further enhance intervention engagement and self-monitoring, participants in the HIWL group will also receive a **Bluetooth-connected body weight scale**. The scale and Carium digital intervention will link electronically; the scales will transmit weight data automatically in a secure fashion to participants' accounts, allowing the participant and his or her providers to view the weight data in real time. We will instruct participants to weigh themselves daily throughout the course of the study.

Continuous glucose monitoring: Thirty participants will receive the HIWL intervention as outlined above and also receive a supply of continuous glucose monitors to use throughout the trial. The CMG we provide will give the patient instant feedback on blood glucose levels and be readable using a mobile phone device or an associated CGM reader (For details of the CGM device, see 8.1 ENDPOINT AND OTHER NON-SAFETY ASSESSMENTS). The data from the CGM will be integrated into the Carium app and used to help guide the patient's actions based on defined care pathways.

Development and refinement of care pathways: We will work with the Carium development team to expand and tailor the standard care pathway for the treatment objectives of this proposal—weight reduction and improved glycemic control. The focus of the care pathway will be on supporting lifestyle change, minimizing risk of adverse events, and providing actionable data to predict higher risk of disengagement. We will build key modules that enable automated guidance based on stage of treatment and anticipated difficulties/challenges that are most likely at a given stage. This process will use participant response to brief surveys and queries to determine which content needs to be delivered and when clinical support (i.e., someone from the clinic team) should be engaged. This will result in provision of content and support when it is most appropriate and in an efficient manner. For example, through this process we can develop content that anticipates GI related side effects of a MR-based diet (e.g., constipation) and provide participants with educational content on how to prevent it in the first 1-2 weeks of treatment. Surveys would be timed to go out when our clinical experience suggests symptoms of constipation might develop. If a survey response indicates that current constipation

prevention measures are ineffective, a team member can engage the participant in a chat session to provide support to resolve the issue before it becomes more distressing and resource intensive (e.g., requiring a call to the center with multiple workflows and provider types engaged to deal with a preventable/predictable side effect). Content can be programmed based on participant characteristics (e.g., on insulin versus only on metformin) so that information can be targeted and highly relevant to the individual user. The pathway will also have key outcome indicators that will roll up into a clinical dashboard shared by the provider team. The indicators will help providers allocate time and attention to those who would benefit most based on pre-set cut points. Over time, we will adjust the cut points based on treatment outcomes to improve the sensitivity and specificity of each indicator.

CONTROL INTERVENTION:

Diabetes self-management education (DSME): The DSME intervention will be administered and delivered at the WFBH Diabetes Center, located next to the Weight Management Center. The diabetes education program is accredited by the American Diabetes Association in recognition of meeting national standards for diabetes self-management education. The goal of the program is to provide participants with information to make informed decisions about how to best integrate diabetes management strategies into their daily lives. Assessment, planning, implementation, and evaluation are the basic components of the diabetes education process. The DSME will be delivered by qualified personnel in group and individual settings. The DSME will be provided over the course of 12 months. Participants will have a variety of learning objectives that are part of the core Comprehensive Diabetes Education Program provided by the WFBH Diabetes and Endocrinology Center. Participants will attend an initial group class or individual appointment in the first month, followed by at least quarterly individual appointments through the next 11 months. Additional appointments may be recommended by the diabetes educator. Participants will be prescribed a weight reducing diet that is 500-750 kcal below estimated total energy expenditure using the Mifflin-St. Jeor equation.²² The dietary plan will focus on carb counting and healthy diet quality, allowing up to 45 g carbs per meal for women and 60 g carbs per meal for men. Similar to the HIWL intervention, the physical activity prescription will be a goal of 180 minutes of moderate intensity activity per week, using a combination of resistance training and aerobic exercise. However, the DSME group will not have exercise training sessions, but we will provide written and oral instructions on strategies in the group and individual counseling sessions to meet the exercise goals.

6.2 FIDELITY

6.2.1 INTERVENTIONIST TRAINING AND TRACKING

Fidelity to treatment impacts reliability and validity of study findings. To ensure consistency of intervention content and delivery, we will use standardized treatment protocols and procedures. A

comprehensive Manual of Operations and Procedures will be developed in the start-up period and distributed to all personnel. Written procedures will exist for assessments, treatment delivery, and monitoring of treatment delivery. Study personnel will be thoroughly trained in the interventions and given corrective feedback in practice sessions. Even among highly trained interventionists, there is a potential for slight deviations from treatment protocol to occur over time, commonly referred to as “intervention drift.” In order to protect against this, regular “booster” training sessions will be conducted. Treatment fidelity will be monitored also by live supervision. The Interventionist will be observed regularly by one of the investigators during group and individual sessions. Live supervision corrects for procedural and intervention drift and enhances adherence to the protocol.

6.3 MEASURES TO MINIMIZE BIAS: RANDOMIZATION AND BLINDING

Participants will be randomized using a web-based protocol for treatment assignment. Once participants are screened as eligible to participate, the study coordinator will submit the participant's study number for treatment assignment via the study web portal. Randomization will be done in blocks of 10, stratified by sex.

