Study Population:	Participants will be individuals 18 and older who have T2DM diagnosed within the past 6 years with a BMI of 27-50 kg/m ² . Participants must have an HbA1c between 6.5-11.9%. Sample size will be 30 participants per treatment group.
Phase* or Stage:	Phase 4
Description of Sites/Facilities Enrolling Participants:	Wake Forest Baptist Health Weight Management Center (WMC) Wake Forest Baptist Health Diabetes Center (DC)
Description of Study Intervention/Experimental Manipulation:	Participants randomized to the HIWL treatment group will be placed on a meal replacement-based weight loss protocol. Our active intervention will be delivered with the aid of a technology platform that will automate portions of the intervention and assist clinicians in tailoring treatment and responding to participant needs in a “just-in-time” manner that we frame as a “data-assisted approach.”
Study Duration*:	15 months
Participant Duration:	12 months

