4 STUDY DESIGN

4.1 OVERALL DESIGN

This project will determine if a data-assisted, high intensity medical weight loss intervention (HIWL) will lead to significant weight loss and diabetes remission in individuals with a BMI 27-50 kg/m² with T2DM of less than 6 years as compared to a diabetes self-management education intervention (DSME). Complete diabetes remission is considered to be achieved when the patient is not taking any anti-diabetes medication for at least 12 months, and the HbA1c is < 5.7%. Partial remission is achieved when the patient is not taking any anti-diabetes medication and has an HbA1c of 5.7-6.4% for at least 12 months. Using a randomized controlled study design, we will randomly assign 90 participants to HIWL, HIWL + CGM, or DSME. Participants assigned to HIWL will receive a high intensity behavioral weight loss intervention delivered using a digital patient engagement platform. Participants will be prescribed a low calorie dietary plan and a recommended physical activity program designed to produce 15-20% weight loss over 12 months. Those assigned to HIWL + CGM will receive the same intervention as HIWL; in addition we will provide them with CGM to use as part of their remote monitoring on a daily basis. Those assigned to DSME will participate in a comprehensive diabetes education program designed to provide education and skills for optimal diabetes management plus lifestyle modification counseling to produce 5% weight loss over the same timeframe. The primary outcome of weight loss will be assessed at 12 months.

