9.2 SAMPLE SIZE DETERMINATION

Power Considerations: Power was estimated assuming a longitudinal framework based on linear mixed models allowing for attrition. The estimated change in weight for the active intervention is 15% at 12 months. The estimated change in weight for the DSME intervention is 3% at 12 months. We anticipate 10% of the study population will be lost to follow up; however, we estimated power based on lost to follow up rates of up to 20%. Using a pooled standard deviation of 6.8% for percent weight loss, we will have > 95% power to detect our hypothesized difference at 12 months with 30 participants per arm.

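### Blocks of 10 cannot be split equally over three arms, and the plan does not say how 30 per arm is to be reached

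*Combined protocol and SAP*

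**What the plan says.** Section 6.3 describes web-based assignment, requested by the study coordinator once a participant is found eligible, and adds: "Randomization will be done in blocks of 10, stratified by sex". It says nothing more about the structure of the list.

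The arm sizes are given elsewhere:

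- Section 4.1: "we will randomly assign 90 participants to HIWL, HIWL + CGM, or DSME".
- Section 1.1: "Sample size will be 30 participants per treatment group".
- Section 6.1.1, on the monitor arm: "Thirty participants will receive the HIWL intervention as outlined above and also receive a supply of continuous glucose monitors".
- Section 9.2 claims "> 95% power to detect our hypothesized difference at 12 months with 30 participants per arm".

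Equal allocation is therefore implied throughout, though never written as a ratio. No section says how ten places are shared among three arms.

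**The concern.** A permuted block gives equal allocation only if its size is a multiple of the number of arms. With three arms, a block of 10 always leaves one place over. Whoever programs the list must invent a rule for that place, and different rules lead to visibly different trials. If the same arm always gets it, that arm ends about a third larger than each of the others (36 against 27).

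Two things are at stake. The first is whether the randomisation can be carried out as written and agrees with the stated arm sizes. The second is smaller and separate. The block size is fixed and printed in the protocol. The arms are plainly distinguishable (meal replacement, daily glucose monitoring, diabetes education), and section 6.3 describes no masking of assignment despite its title. Someone who tracks assignments within a sex stratum could work out some of the later places in a block.

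**Working it through.** **Inputs.** Block size 10 and two sex strata (section 6.3); 90 participants and three arms (4.1); 30 per arm (1.1, 9.2). For power, section 9.2 expects a loss of 15% of body weight with the active treatment and 3% with education, takes 6.8% as the pooled standard deviation, and allows for loss to follow-up of up to 20%. Two inputs are assumptions. The documents give no sex split, so 50% women is assumed unless stated. Section 9.2 gives no significance level, so two-sided 0.05 is assumed.

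**Step 1: the plan's own power figure.** The difference is 15 − 3 = 12 points. Power ≈ Φ(12 / (6.8 × √(1/n₁ + 1/n₂)) − 1.96).

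- 30 v 30: 12 / (6.8 × √(2/30)) = 6.83; Φ(4.87) is above 99.99%.
- 24 v 24 (20% loss): 6.11; Φ(4.15) is above 99.99%.

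The claim of more than 95% is reproduced with a wide margin.

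**Step 2: block arithmetic.** 10 = 3 × 3 + 1, so the nearest composition to equal is 4:3:3. 90 / 10 = 9 complete blocks.

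- *Fixed extra arm:* 9 × 4 = 36 and 9 × 3 = 27, giving 36/27/27. Any single composition repeated nine times gives totals that are multiples of 9, so 30 cannot arise from complete blocks.
- *Random extra arm:* 30/30/30 requires each arm to be drawn exactly three times in nine. The probability is 9! / (3! 3! 3!) / 3⁹ = 1680 / 19683 = 8.5%.
- *Rotating extra arm:* each arm gets the extra place three times, 3 × 4 + 6 × 3 = 30. This is guaranteed only if each sex stratum is a multiple of 30, because the rotation runs within strata.

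**Step 3: simulation with two sex strata, incomplete last blocks allowed.** The gap is the largest arm minus the smallest. The guess column is the share of assignments called correctly by someone who always names the arm least used so far in the stratum.

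| Scheme | Exactly 30/30/30 | Gap ≥ 4 | Least-used-arm guess correct |
|---|---|---|---|
| Blocks of 10, fixed 4:3:3 | 0% (mean 36/27/27) | ≈100% | 43% |
| Blocks of 10, random tenth place | about 6–7% | about 44% | 45% |
| Blocks of 10, rotating tenth place | about 9–17% | about 14–19% | 49% |
| Random 3 and 6 | about 42% | 0.4% | 57% |
| Random 6 and 9 | about 29% | about 3% | 54% |
| Random 6 and 12 | about 26% | about 7% | 52% |

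For the rotating rule, the gap figure is about 14% if the starting arm is drawn separately in each stratum, and about 19% if both strata start with the same arm.

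**Step 4: power at the unequal splits.**

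- 27 v 27: 12 / (6.8 × √(2/27)) = 6.48; Φ(4.52) is above 99.99%.
- 21.6 v 21.6 (27 per arm less 20%): 5.80; Φ(3.84) = 99.99%.
- An assumed extreme of 4:4:2, giving 36/36/18, less 20% (14.4 v 28.8): 5.47; Φ(3.51) = 99.98%.

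**The case against.** The strongest reply is that the plan never says the composition is a fixed 4:3:3. Ninety is exactly nine blocks of 10, and a rotating extra place can finish at 30/30/30. A reader might infer that 30 per arm is ruled out, or that 36/27/27 is what this trial will get. The documents support neither, because both rest on a composition that section 6.3 does not give. This part of the reply stands. It does not remove the gap: the rotating rule is also nowhere in the documents, and it guarantees 30 per arm only at sex splits that the trial does not control.

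A reader might also infer that the trial loses power, since section 9.2 counts on 30 per arm. Step 4 shows that it does not. Unequal arm sizes also do not by themselves bias the analysis of covariance in section 9.4.1. The first hypothesis in section 9.1 takes the two weight-loss arms together against education; if they are pooled, that contrast is about 2:1 in any case.

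Two further points stand. Blocks divisible by three do not guarantee 30/30/30 either, because strata can end mid-block. And a naive guesser does somewhat better with them than with blocks of 10. Even someone who knows the block boundaries and a fixed 4:3:3 composition is right only about 53% of the time with blocks of 10. Predictability therefore does not add much weight to the point, and it argues against very small blocks as the remedy.

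Finally, the block size might be a remnant of a two-arm design, since section 4.2 speaks of two interventions. The documents do not say so.

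**Conclusion.** The point holds as a specification and balance error. A block of 10 is incompatible with equal allocation over three arms within a block, and the documents do not show how 30 per arm is reached. Depending on the unstated rule, the consequence runs from about 36/27/27 (fixed extra place), through a gap of at least 4 in about 44% of trials (random), to such a gap in about 14–19% (rotating). These figures assume 90 randomised and 50% women; other sex splits change the percentages, but not the fact that ten does not divide by three.

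Power stays above 99.9% at 27 versus 27 with 20% loss, given the difference and standard deviation in section 9.2 and a two-sided 0.05 level. The point should be corrected because section 6.3 cannot be programmed as written and the change is cheap. It does not threaten the primary comparison.

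**What to change.** In section 6.3, replace the sentence on blocks with a statement that allocation is 1:1:1 in permuted blocks whose sizes are multiples of three, stratified by sex. Preferably let the size vary at random between larger values, for example 6 and 9, or 6 and 12. Blocks of 3 and 6 give tighter balance but are the easiest to guess. Keep the sizes in a restricted randomisation file and out of the protocol, because assignment is open-label.

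The cost is one sentence and a regenerated list, with no extra participants. There is a small downside: a least-used-arm guess is right about 52–54% of the time, against 43–49% with blocks of 10. A gap of 4 or more will still occur in about 3–7% of trials, so the arm sizes should be described as targets.

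If randomisation has already started, document the composition actually used, make the change by amendment, and apply it only to the remaining assignments.
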